Once the tACS began, participants completed a series of Stimulation Tasks designed to engage episodic memory. First, they completed the Mnemonic Discrimination Task (MDT³), which assesses high-fidelity long-term memory (LTM). During each tACS session, participants completed the MDT with unique stimuli consisting of common real-world items. This resulted in eight versions of the MDT, which were counterbalanced in order between participants (forwards or backwards order). Immediately after the tACS began, participants completed the encoding portion of the MDT task. During encoding, participants were cued first with “will the object fit inside a lady’s shoe box?” Following the prompt, participants viewed 39 items in a random order and responded to the question for each item with an untimed button press. Next, participants were presented with a second cue “can you carry the object across the room using only one hand?” Participants then responded to this question following a random presentation of the same 39 items. All items were presented for 2500 ms followed by a screen that listed the button press responses (“D” for yes, “K” for no). A fixation cross was presented on the screen for 1000 ms between trials. The MDT encoding portion of the task is timed to last 8-10 minutes. All versions of the MDT task were created using PsychoPy.

Following the MDT encoding period, participants completed 20 minutes of a commercially available tablet game, Spot the Difference. This game was chosen so that participants are mentally engaged in a visual search task that has no interference with recently encoded items from the MDT task and not a task that would evoke stress due to task difficulty. Participants completed this task at their own pace and advanced to new images without any score being kept. Next, participants completed the semantic fluency task with three letters and a category similar to the cognitive testing with F, A, S, and animals (see above). Here, we created 8 unique sets each consisting of three letter prompts and one semantic category. Thus, the fluency task was not repeated across any of the tACS sessions and was different from the fluency tasks used as our Cognitive Tasks outcome measures. Participants were instructed to name as many items as possible.

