During the final 10 minutes, participants completed three MDT test blocks where they viewed 13 items seen during encoding, 13 items that were an alternate (similar) version of the encoded items, and five novel lures. For each item participants responded as to whether they were the same exact item from the encoding task from the beginning of stimulation. Each item was viewed for 2500 ms and followed by a screen where participants would respond whether the item was definitely old (“D” key), maybe old (“F” key), maybe new (“J” key), or definitely new (“K” key). A fixation cross was presented on the screen for 1000 ms between trials. The order of the target, lure, and novel items was random within each of the three testing blocks. In total, the tasks for the participant to complete during stimulation are equal to the length of the tACS session (1 hour).

Data Processing and Statistical Analysis.

Given the relatively small number of participants this study, we used non-parametric tests for all statistical analyses to reduce influence from potential extreme values. Changes in outcome metrics were assessed with non-parametric Wilcoxon sign-ranked tests. We also report rank-biserial correlations (r_{rb}) to represent effect sizes of these changes, similar to Cohen's d . We set a significance threshold of $p < 0.05$ and report non-significant 'trends' at $p < 0.10$. As this is a hypothesis-generating pilot study, we did not correct for multiple comparisons for each test conducted.

Primary Outcomes.

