Blood was collected by phlebotomy in EDTA tubes and centrifuged at 2,000 g for 10 min at 4°C. Plasma was then aliquoted in 500 microliter polypropylene tubes, and stored at -80°C until analyses, with an average needle-to-frozen storage time < 2 hours. Plasma was analyzed according to vendor protocols, using commercially available kits Neuro 4-PLEX E [amyloid β_{1-42} (A β 42), amyloid β_{1-40} (A β 40), neurofilament light chain (NfL), and glial fibrillary acidic protein (GFAP)] and P-tau181 for single molecule arrays in an HD-X analyzer (Quanterix, Billerica, MA). Lowest level of quantification and average coefficient of variations were 0.378 pg/mL, 4.1% for A β 42; 1.02 pg/mL, 3.5% for A β 40; 0.4 pg/mL, 4.3% for NfL; 2.89 pg/mL, 4.6% for GFAP; and 0.4 pg/mL, 10.1% for P-tau181. Analyzed samples underwent only one thaw cycle prior to use. Samples were run in duplicate, with kits from the same lot. Following analysis, we were able to measure the picograms per milliliter (pg/mL) of each of the three AD biomarkers at both time points, to quantify stimulation-related changes in AD biomarker levels between the two time points.

Exploratory Behavioral Outcomes.

We examined changes in MDT task performance as a non-registered exploratory measure, focusing on the changes in the lure discrimination index (LDI, proportion lure correct rejection—proportion novel false alarm) between the initial tACS session and final tACS session. Changes in performance were assessed with a Wilcoxon sign-rank test. As the MDT task was completed concurrently with the tACS, it is important to note that changes in MDT performance reflect gains during tACS from repeated test performance, rather than transfer to an untrained task, as with our secondary outcomes. In addition to examining changes in this study population, however, we also compared initial and final LDI performance in these MCI participants to a placebo training control group of healthy older adults from a previous study, where no training-related MDT gains were expected. For this analysis, we compared both initial and final performance between these groups using non-parametric Mann-Whitney U tests.

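### The MDT lure discrimination index adds response bias instead of removing it and uses no target responses, so a change or group difference in it cannot be put down to memory on this index alone

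*Combined protocol and SAP*

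**What the plan says.** The Exploratory Behavioral Outcomes section defines LDI as "proportion lure correct rejection—proportion novel false alarm". Change from the first to the last tACS session is tested with a Wilcoxon signed-rank test. Initial and final LDI are also compared, by Mann-Whitney tests, with "a placebo training control group of healthy older adults from a previous study". No other MDT measure is named. The section does caution that "changes in MDT performance reflect gains during tACS from repeated test performance" and not transfer to an untrained task.

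The task itself is described under Stimulation Tasks, where the MDT is introduced as one "which assesses high-fidelity long-term memory (LTM"). At encoding, "participants viewed 39 items in a random order". Three test blocks follow, with "13 items seen during encoding, 13 items that were an alternate (similar) version of the encoded items, and five novel lures". The judgement required is stated as: "For each item participants responded as to whether they were the same exact item from the encoding task". The answers allowed are "definitely old (“D” key), maybe old (“F” key), maybe new (“J” key), or definitely new (“K” key"). There is no key for 'similar', and the text does not say how the four keys are split into old and new.

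**The concern.** Subtracting a novel-item rate corrects for bias only if it is the rate of the same response as in the first term. Here the first term is a 'new' rate and the subtracted term is an 'old' rate, so the subtraction reinforces the bias.

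High-fidelity memory means telling a studied item from its similar version. Rejecting lures shows this only if true targets are still accepted, and no planned measure checks that.

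At stake is the reading of the within-group LDI change and of the comparison with healthy controls. With eight tACS sessions, participants have met this test format seven times before the last one, so a shift in criterion is plausible, though nothing in the documents demonstrates it. The control comparison sets people with aMCI against healthy adults from another study, so equal criteria cannot be presumed there either. The caveat about repeated testing does not deal with bias.

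**Working it through.** **Inputs from the document.** Old/new keys only; the LDI formula; 13 completers; significance at p < 0.05 (sidedness not stated, two-sided assumed). Reading 13/13/5 as items per block gives 3 × 13 = 39 targets, 3 × 13 = 39 lures and 3 × 5 = 15 novel items, which fits the 39 encoded items. The plan states no LDI value or power figure, so there is nothing of its own to reproduce.

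**Step 1: algebra, with no assumed data.** A lure correct rejection is a 'new' response; a novel false alarm is an 'old' response.

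LDI = P(new, given lure) − P(old, given novel) = P(new, given lure) + P(new, given novel) − 1.

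This holds for any split of the four keys that is applied to both item types. A person with no memory who says 'new' with probability b scores b − (1 − b) = 2b − 1: that is −1 at b = 0, 0 at b = 0.5, 0.5 at b = 0.75 and 1 at b = 1. Hits minus lure false alarms is 0 for every such person.

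**Step 2: size in closed form.** All strengths, criteria and shifts from here on are assumed. Use an equal-variance signal-detection model: novel mean 0, target mean t, lure mean l, and 'old' when strength exceeds the criterion c. Then LDI = Φ(c − l) − [1 − Φ(c)]. Start at c = t/2 and raise c by 0.25 with memory fixed:

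| t / l | LDI before | LDI after | Rise |
|---|---|---|---|
| 1.0 / 0.5 | 0.191 | 0.372 | 0.181 |
| 1.5 / 0.9 | 0.214 | 0.381 | 0.167 |
| 2.0 / 1.0 | 0.341 | 0.493 | 0.152 |

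**Step 3: two causes, nearly the same LDI (t = 1.5, l = 0.9, c = 0.75).**

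| | Start | Criterion +0.25 | Lure strength 0.9 to 0.5 |
|---|---|---|---|
| LDI | 0.214 | 0.381 | 0.372 |
| Hits | 77% | 69% | 77% |
| Lure false alarms | 56% | 46% | 40% |
| Novel false alarms | 23% | 16% | 23% |

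The separate rates tell the two apart; LDI does not.

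**Step 4: a gain in target memory.** With the criterion held at 0.75, raising t from 1.5 to 2.0 lifts hits from 77% to 89% and d′ from 0.6 to 1.1. LDI stays at 0.214, because targets are not in it.

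**Step 5: Wilcoxon test with memory unchanged.** Simulation: 2,000 studies per cell, n = 13, 39/39/15 trials, exact test, the three strength sets above, between-person SD 0.3 for target strength and 0.25 for criterion. Share of studies with p < 0.05:

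| Mean criterion shift | SD of individual shifts | LDI | d′ |
|---|---|---|---|
| 0 | 0.25 | 4–5% | 5% |
| +0.10 | 0.25 | 13% | 5% |
| +0.25 | 0.25 | 55–57% | 4–5% |
| +0.25 | 0 | 81–83% | 4–6% |
| +0.50 | 0.25 | 98–99% | 4–5% |
| −0.25 | 0.25 | 58–60% | 5–6% |

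Other assumed strengths (target 1.75, lure 1.0, individual shifts not varying) give 83% for LDI and 5% for d′ at +0.25.

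**Step 6: Mann-Whitney test with equal memory and one group's criterion 0.25 higher.** The number of controls is not given. LDI is significant in 41–44% of studies with 13 controls and 59–62% with 40; d′ in 4–6%.

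**The case against.** The algebra is hard to dispute; the case against concerns weight and evidence.

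- *The outcome is exploratory, non-registered and already caveated.* True, and it limits the impact. But the caveat separates repeated-test gains from transfer. It still treats a rise as a gain in performance.
- *The plan says it focuses on LDI, which does not rule out hit rates.* Fair. The exact statement is that no target-based measure is named.
- *LDI misses a target-memory gain only if the criterion stays put.* Correct as a condition. If c follows t/2, it moves from 0.75 to 1.0 and LDI goes from 0.214 to 0.381. That is exactly the value a pure criterion shift gives in Step 2, so LDI is again responding to the criterion and not to target memory.
- *No shift is shown, and its direction is unknown.* This stands. No feedback is described and stimuli differ between sessions. The simulated rates follow from the assumed shift, and at +0.10 the rate is only 13%. A downward shift would lower LDI and could hide a real gain.
- *The control comparison is already weak,* since it sets aMCI with stimulation against healthy adults from another study. This also stands; bias is an additional obstacle there.
- *Adding post hoc tests to an uncorrected set increases flexibility.* Also fair. That is why the written LDI should stay visible and the additions be labelled.

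**Conclusion.** The concern holds. As written, LDI increases with any tendency to answer 'new', through both of its terms, and takes no account of target responses. That conclusion rests only on the response keys and the formula. If novel false alarms are close to zero, the added part is small, but LDI then approaches the raw lure correct-rejection rate, which is not corrected for bias either.

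The sizes are illustrations under assumed signal-detection values. A 0.25 SD shift is enough to make a null memory effect significant in more than half of studies with 13 participants. Whether any shift happened is unknown, and the plan as written could not tell. The problem should be fixed, but its reach is limited to this exploratory outcome and its control comparison. The primary and registered secondary outcomes are unaffected.

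**What to change.** 1. At the least, report target hit, lure false-alarm and novel false-alarm rates beside LDI, for both sessions and both groups.
2. State how the four keys are split into old and new. With that split, score target-versus-lure d′ from the stored responses (add 0.5 to each count and 1 to each denominator). Use the ROC area from the four ratings as a check.
3. Analyse d′ with the same Wilcoxon and Mann-Whitney tests, label it post hoc, and keep the written LDI alongside.
4. If the controls' target responses were not kept, show their lure and novel false-alarm rates separately and state that the group comparison cannot separate memory from bias.

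The cost is re-scoring stored responses and a few sentences; no new data are needed. The downsides should be stated:

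- This is a post hoc departure from the written formula, and the documents do not say whether the controls' target responses exist.
- d′ is only approximately free of criterion. With a target SD of 1.25 it rejects in 6–7% of studies at a +0.25 shift and 11–12% at +0.5, against 55–57% and 99% for LDI. The ROC area reaches 12% for a −0.25 shift at 2.0/1.0.
- Power for a real lure-rejection gain (lure strength −0.4, no mean shift) is 78–85% for d′ and 41–49% for LDI when individual criteria vary by SD 0.25. Without that variation it is 79–88% and 69–80%, with no advantage at 2.0/1.0 (79% against 80%).

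### The exploratory LDI analysis compares MCI with controls on level at the initial and final sessions, but does not test whether the groups changed by different amounts (minor)

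*Combined protocol and SAP*

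**What the plan says.** The Exploratory Behavioral Outcomes section introduces the measure with its status: "We examined changes in MDT task performance as a non-registered exploratory measure". The analysis is framed as change from the initial to the final tACS session, "focusing on the changes in the lure discrimination index", and the test is paired: "Changes in performance were assessed with a Wilcoxon sign-rank test".

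The plan then warns that "changes in MDT performance reflect gains during tACS from repeated test performance". Directly after this caveat it adds a comparison group, described as a "placebo training control group of healthy older adults from a previous study, where no training-related MDT gains were expected". The method for that comparison is: "For this analysis, we compared both initial and final performance between these groups using non-parametric Mann-Whitney U tests".

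Data Processing and Statistical Analysis prescribes Wilcoxon tests for changes and says of multiplicity: "As this is a hypothesis-generating pilot study, we did not correct for multiple comparisons for each test conducted". Exploratory Neural Analyses adds Wilcoxon tests and Spearman correlations. No section describes a test of change within the controls, a test of MCI change against control change, or a group-by-time analysis.

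**The concern.** The question posed is about change, and the control group is characterised by its expected lack of gain, which makes it a natural reference for change. Yet the controls enter only two comparisons of level. Their lack of gain is an expectation; no test of it is described.

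Two level tests do not answer a change question. A significant difference at the start and a non-significant one at the end can arise when both groups gain equally, because each test has limited power and either can miss a gap that is still there. Conversely, a real difference in gain can leave both level tests non-significant.

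Among the memory measures (CVLT, PAT, MDT), this is the only one compared with another group in a single-arm study. Little else is at stake, since no primary or secondary conclusion depends on it.

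**Working it through.** The plan gives no power or error figure for this analysis, so there is none to reproduce. The finding rests on the text; the arithmetic only shows why the two kinds of test differ.

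**What each test addresses.** Let M1, M2 be the MCI levels and C1, C2 the control levels at the initial and final sessions.
- Wilcoxon test: M2 − M1.
- Initial Mann-Whitney test: M1 − C1.
- Final Mann-Whitney test: M2 − C2.
- Difference in gain, not tested: (M2 − M1) − (C2 − C1), which on means equals (M2 − C2) − (M1 − C1).

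The two level gaps therefore imply an estimate of the difference in mean gain, but their two p-values do not test it. Its precision depends on the within-person correlation r, which level tests ignore: with SD 1 at each session, the SD of change is √(2(1 − r)). For r = 0.7 this is √0.6 = 0.77, so a 0.8 SD gain equals 0.8/0.77, or about 1.03 change SDs.

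**Illustration.** From the documents: 13 MCI completers (Participants), taken to have LDI at both sessions, and the 0.05 threshold (Data Processing and Statistical Analysis), taken as two-sided. Assumed: normal scores with SD 1, 20 controls, MCI 0.8 SD lower at the start, r = 0.7. The pattern means: MCI significantly lower at the start, no significant difference at the end, and a significant upward Wilcoxon test in MCI.

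| True gain, MCI / controls (SD) | True final gap (SD) | Pattern | Change test favours MCI |
|---|---|---|---|
| 0 / 0 | 0.8 | 1% | 2 to 3% |
| 0.5 / 0.5 | 0.8 | 11% | 2% |
| 0.8 / 0.8 | 0.8 | 13% | 2% |
| 0.5 / 0 | 0.8 − 0.5 = 0.3 | 30% | 39% |
| 0.8 / 0 | 0.8 − 0.8 = 0 | 50% | 77% |
| 0.8 / 0.3, practice only | 0.8 − 0.5 = 0.3 | 43% | 38 to 39% |

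Repeat runs agreed to within about two percentage points. The pattern rate is the risk of misreading the results; it is not the error rate of any planned test.

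**Reading the rows.** With equal gains, the change test favours MCI at about its nominal one-sided rate of 2.5%, while the pattern appears several times as often. The last row is the limit of the remedy: if controls gain less only because they took the test fewer times, both routes point to MCI about equally often.

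**The opposite error.** With a smaller starting gap of 0.4 SD and a 0.8 SD gain in MCI only, each level test is significant in 14 to 23% of runs and the change test in 46 to 99% (13 to 50 controls, r from 0.5 to 0.85).

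**The case against.** The strongest reply is that no stated inference is wrong. The plan says it compared initial and final performance, and Mann-Whitney tests answer that validly. A reader might infer that the plan claims the MCI group caught up with controls or gained more than they did, or that the level tests carry an inflated error rate. The documents support neither reading. No such conclusion is drawn, and an error rate for a claim of differential change cannot be charged to tests that are not said to support that claim. This part of the reply stands. What remains is that placing the controls straight after the repeat-testing caveat invites a reader to use them to interpret change.

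Second, the plan already labels the measure exploratory, calls the study hypothesis-generating and attributes MDT change to repeated testing. That stands too, and keeps the point minor.

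Third, equal gains in both groups sit uneasily with the plan's expectation of no training-related gain in controls. That expectation is untested and does not exclude gains from repeat testing, so the case is possible, but it is one assumption among several.

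Fourth, a change test has its own weakness. MCI participants took the MDT eight times (Stimulation Tasks), and the controls' number is not given. If it was lower, the change test loses its advantage, as the last row of the table shows. Diagnosis and study differ in any case. A reader might infer that comparing gains would show an effect of tACS; it would not.

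**Conclusion.** The point holds as a minor, inexpensive improvement. The plan tests LDI change only within MCI and compares MCI with controls only on level at two sessions, so the control group is not used to judge whether MCI changed more. The level tests are valid descriptions, and the plan claims no more from them. Losing a significant difference at the final session would not be evidence of a greater gain.

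Confidence in the reading of the text is high. The size is illustrative only: apart from the 13 completers, every input to the model is assumed. With equal gains the change test is clearly the safer guide (about 2% against 11 to 13% for the pattern). With unequal exposure it is not (38 to 39% against 43%). No primary or secondary conclusion is affected.

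**What to change.** If control scores are paired by person, add one Mann-Whitney test on each person's LDI change (final minus initial), MCI versus control, with the Hodges-Lehmann difference and 95% confidence interval. Label it exploratory and post hoc, and report the control group's own change. Keep the Wilcoxon test, and keep the initial and final level comparisons as descriptive.

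Report the control n and the number of MDT administrations, and say what initial and final mean for controls. State that:
- a difference that is no longer significant at the final session is not evidence of a greater gain;
- the comparison does not isolate tACS;
- if controls had fewer than eight administrations, it does not separate gain from repeat testing.

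The cost is a few sentences and one further uncorrected exploratory test. The text implies that both control time points exist, but does not say that they are linked by person. If they are not, the wording changes alone suffice.

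The downsides are real. The test is post hoc, since the document already reports on completers, and the result may be less favourable. Precision is low: under the assumed model the 95% interval has a mean half-width of about 0.36 to 0.85 SD (13 to 50 controls, r from 0.5 to 0.85). The groups still differ in diagnosis, study and possibly MDT exposure.

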Participants completed two MRI sessions with the same protocol prior to and following the tACS intervention (i.e., during the pre- and post-tACS phases, respectively). All data was collected by a Siemens 3T MAGNETOM Trio MRI using a 64-channel head coil. First, high-resolution T1-weighted anatomical images were acquired (1 x 1 x 1 mm voxel size, FOV = 160 x 240 x 256 mm, repetition time (TR) = 2300 ms, echo time (TE) = 3 ms, flip angle (FA) = 9°). For MRS, two voxels were placed in the left Pars, and left Hipp (3x3x2 cm each) based on the T1 structural scan. We then collected GABA-edited MEGA-PRESS scans (TR/TE = 2000/68 ms, 128 averages, FA = 90°), with editing pulses at 1.9 edit-ON and 7.2 edit-OFF ppm. The edit-ON and edit-OFF differences yield the peaks affected by the editing pulses.

Next, participants completed approximately six-minutes of eyes-closed resting-state functional MRI (rs-fMRI) using a T2*-weighted echoplanar imaging (EPI) sequence with the following parameters: 560 volumes, TR = 850 ms, TE = 32.8 ms, FA = 45°, in-plane resolution = 2.2 mm², 66 total 2.2 mm slices using a multiband acceleration factor of 6. Participants were instructed to close their eyes, remain awake, and be as still as possible. Last, DTI data was collected with 10 non-diffusion weighted images (b = 0 s/mm²) followed by 96 diffusion weighted images (b = 2500 s/mm²; TR = 2420 ms, TE= 72.2 ms, and FA = 85°). One participant did not have usable rs-fMRI at their post-tACS session due to imaging artifacts, resulting in usable datasets from 12 participants for these analyses. One participant did not have baseline DTI data due to time constraints in the MRI, resulting in usable datasets from 12 participants for these analyses.

Phlebotomy.

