Further, we examined changes in IADL from pre-tACS to post-tACS as an exploratory measure on each of the categories: bathing, dressing, grooming, mouth care, toileting, transferring bed/chair, walking, climbing stairs, eating, shopping, cooking, managing medications, phone use, housework, driving/transport, and managing finances. Specifically, we measured change in the IADL metrics from the pre-tACS to post-tACS session by measuring the average rating across all IADL categories and comparing these in non-parametric Wilcoxon signed-rank tests between the pre-tACS baseline and post-tACS follow-up sessions.

Resting State Functional MRI.

We conducted exploratory analyses on the rs-fMRI data collected during the pre- and post-tACS scans. Standard preprocessing of MRI data for functional connectivity analyses was carried out with AFNI and FreeSurfer. First, participants' T1-weighted anatomical images were skull-stripped and segmented into gray matter, white matter, and cerebrospinal fluid (CSF) using FreeSurfer. Next, EPI data was pre-processed using afni_proc.py in AFNI. First, the de-spike option was applied to interpolate extreme outlier timepoints from the BOLD signal intensity time courses. Next, the EPI data was motion corrected (aligning each EPI volume to the volume with the minimum outlier fraction), co-registered to the T1-weighted anatomical image, warped to MNI space, and resampled to an isotropic resolution of 2 mm³. Further, we implemented noise reduction by regressing out several 'nuisance' variables: (1) 12 motion regressors (6 realignment parameters and their derivatives), (2) voxel-wise local white matter regressors using AFNI's fast ANTATICOR method, and (3) the top 3 principal components from lateral ventricle voxels. EPI data was also bandpass filtered (0.01-0.10 Hz) and volumes with excessive motion (> 1 mm root mean square motion) and the volume prior were censored. Nuisance regression, bandpass filtering, and censoring were performed in a single step.

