To measure functional connectivity, we quantified Pearson's correlations (and applied a Fisher z-transform) between ROI timeseries from Pars, IPL, and Hipp (left and right) during the baseline and follow-up MRI sessions. Pars and Hipp ROIs were automatically output from the MRS scan (see below) and we generated an additional IPL ROI in FSL. We copied each left hemisphere mask to the right hemisphere to generate masks for all six regions. We calculated functional connectivity as the average connectivity between each ROI pair between and within hemispheres (e.g., IPL-Hipp connectivity calculated as the average of right IPL-Hipp, left IPL-Hipp, right IPL – left Hipp, and left IPL – right Hipp). We note that RSFC for one participant had relatively high values at baseline for each ROI pairing (average RSFC: 0.64) compared to the other participants, despite having no visible artifacts or excessive motion. Importantly, due to

technical issues, this participant did not have baseline MRS or DTI measures and therefore did not overly influence correlation results with those metrics.

Magnetic Resonance Spectroscopy.

Proton 1H MRS data was collected in two ROIs (left Pars and left Hipp). MRS data from our third ROI (IPL) was not collected due to time constraints in the scanner. During the second MRI session we duplicated voxel placement based on images from the first MRI session. All GABA and Glx concentrations were analyzed using GANNET 3.1, which is a specialized toolbox for Matlab designed to analyze GABA by calculating the area under the curve. The E/I ratio of Glx to GABA within ROIs was calculated (Glx/GABA+, both CSF-corrected with a water reference file). This ratio measured the excitatory/inhibitory balance within the ROI at both the pre-tACS and post-tACS MRI sessions. Two participants had poor shimming at baseline and were excluded from analyses, resulting in usable datasets from 11 participants for these analyses.

Diffusion Weighted Imaging.

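### The resting-state Hipp and Pars regions come from 18 cm³ spectroscopy voxels with no described trimming, so Hipp connectivity cannot, under the stated rule, be attributed to the hippocampus

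*Combined protocol and SAP*

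**What the plan says.** The Magnetic Resonance Imaging section describes the spectroscopy placement: "two voxels were placed in the left Pars, and left Hipp (3x3x2 cm each) based on the T1 structural scan".

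The Resting State Functional MRI section takes the Pars and Hipp regions for connectivity from that scan: "Pars and Hipp ROIs were automatically output from the MRS scan (see below". The IPL region was made separately in FSL. For the other hemisphere: "We copied each left hemisphere mask to the right hemisphere to generate masks for all six regions". Correlations were then computed "between ROI timeseries from Pars, IPL, and Hipp (left and right) during the baseline and follow-up MRI sessions". Each pair's value is the average of four links, two within and two between hemispheres.

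The same section says that each T1 image was "segmented into gray matter, white matter, and cerebrospinal fluid (CSF) using FreeSurfer". Local white-matter signal and three ventricle components were regressed out of the functional data. It does not say that the region masks were cut to grey matter or to the structure they are named after.

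On one participant it reports: "RSFC for one participant had relatively high values at baseline for each ROI pairing (average RSFC: 0.64". It adds, citing technical issues, that "this participant did not have baseline MRS or DTI measures and therefore did not overly influence correlation results with those metrics". The Magnetic Resonance Spectroscopy section lists two exclusions, both for poor shimming at baseline, leaving 11 datasets. The Magnetic Resonance Imaging section lists one missing baseline DTI scan, put down to lack of scanner time, leaving 12.

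**The concern.** A spectroscopy voxel is a rectangular block. It does not follow the outline of the structure it is placed on. If the block itself is the connectivity region, the time series labelled Hipp averages hippocampus with whatever else lies in the block. The right-hemisphere regions are copies of the left ones and are not described as fitted to right-hemisphere anatomy.

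This matters because the results are meant to be read anatomically. The Neuromodulation section names Hipp, IPL and Pars as stimulation targets. The Diffusion Weighted Imaging section picks tracts that serve these regions, including the fornix as the hippocampal outflow. The Exploratory Neural Analyses section correlates outcomes with the neural metrics that changed significantly. If the label is not secured, neither a change nor a null says anything specific about the hippocampus.

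A second, smaller matter is that one participant has baseline connectivity for every region pair but no baseline MRS measures. The plan does not say where that participant's Pars and Hipp regions came from.

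**Working it through.** **Inputs from the documents.** Voxel 3 × 3 × 2 cm (Magnetic Resonance Imaging); 13 completers (Participants); two MRS exclusions and 11 usable (Magnetic Resonance Spectroscopy); one missing baseline DTI and 12 usable, and 12 usable resting-state datasets (Magnetic Resonance Imaging).

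**Assumed, not in the documents.** Hippocampal volume *h* of 2 to 5 cm³ per side; for a sensitivity check, a grey-matter fraction *g* of 0.4 to 0.7 within the voxel.

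1. *The plan's own counts.* MRS: 13 − 2 = 11. DTI: 13 − 1 = 12. Resting-state: 13 − 1 = 12. All three reproduce.

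2. *Mask volume.* 3 × 3 × 2 = 18 cm³.

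3. *Largest possible hippocampal share of an untrimmed mask*, with the whole structure inside the voxel: *h* / 18.
   - *h* = 2: 2/18 = 11.1%
   - *h* = 3: 3/18 = 16.7%
   - *h* = 4: 4/18 = 22.2%
   - *h* = 5: 5/18 = 27.8%

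   So 72% to 89% of the volume is other tissue, or more if part of the hippocampus lies outside the voxel. For hippocampus to make up half of the mask, it would have to fill 0.5 × 18 = 9 cm³.

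4. *If the mask had been cut to grey matter*: *h* / (18 × *g*).
   - Lowest: 2 / (18 × 0.7) = 2/12.6 = 15.9%
   - Highest: 5 / (18 × 0.4) = 5/7.2 = 69.4%

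   Whether the mask was trimmed therefore decides whether hippocampus can be the larger part of it.

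5. *Reach.* All three pairs (Pars-Hipp, IPL-Hipp, Pars-IPL) use at least one MRS-derived region, and two of the three use Hipp. Of the four links averaged per pair (left-left, right-right, left-right, right-left), three use at least one copied right-hemisphere mask.

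6. *The participant with no baseline MRS measures.* If this participant were additional to the two poor-shim exclusions, usable MRS would be 13 − 2 − 1 = 10, not 11. The stated count fits if this participant is one of those two. Poor shimming implies that a voxel was placed, so a mask could exist although the spectrum was unusable. The reasons given still differ: technical issues against poor shimming for MRS, and technical issues against lack of time for DTI. Only one baseline DTI scan is listed as missing.

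**The case against.** The strongest defence is that regions matched to the MRS voxels are a deliberate choice. They allow connectivity to be compared with the Glx/GABA+ ratio in the same tissue. The plan discloses both the source of the regions and the copying. The functional data were warped to MNI space, which makes copying to the other side less arbitrary. The analysis is exploratory, in a study that calls itself a hypothesis-generating pilot. All of this stands. It makes the voxel regions defensible as voxel regions, so a reader who concludes that the definition is simply wrong for all participants goes too far. It does not make the anatomical label safe.

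Two stronger readings are tempting, and the documents do not support either:

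- *That Hipp connectivity is mostly signal from outside the hippocampus.* The 11% to 28% is a share of volume, not of signal. It rests on an assumed hippocampal size and an untrimmed mask. Trimming is not described, but that silence does not prove there was none. The white-matter and ventricle regressors also reduce signal from non-grey tissue, though they are not aimed at neighbouring grey matter.
- *That one participant's regions cannot have come from a baseline MRS scan.* The text says "technical issues, this participant did not have baseline MRS or DTI measures"; it is measures that were missing. The count of 11 fits a participant whose voxel was placed but whose spectrum was unusable. Masks shared across participants are also possible, since the plan does not say whether masks were individual.

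A further fair objection is that RSFC values have already been seen. Making new regions the main analysis now would add analytic freedom where there is no multiplicity correction. That argues for reporting anatomical regions beside the existing ones, not in their place.

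**Conclusion.** The concern holds in a limited form. The connectivity regions for Pars and Hipp are output from 18 cm³ left MRS voxels and copied to the right, with no described restriction to grey matter or to the named structure. If the masks are untrimmed, and with an assumed hippocampal volume of 2 to 5 cm³ per side, hippocampus is at most 11% to 28% of the Hipp mask. A change or a null in Pars-Hipp or IPL-Hipp connectivity then cannot be attributed to the hippocampus. For Pars the same question is open, but the documents give nothing from which to size it.

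For the participant with baseline RSFC but no baseline MRS measures, the finding is only that the region source is unstated and the reasons for missing data need reconciling.

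The effect is confined to the exploratory RSFC tests and the correlations built on them. The primary feasibility and tolerability outcomes and the secondary cognitive and plasma outcomes are unaffected.

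**What to change.** 1. State that the Pars and Hipp regions are MRS-voxel masks, whether they were individual or shared, and whether they were trimmed. Intersect them with the grey-matter segmentation already made, and report how much of each mask is grey matter and how much is the named structure.
2. Repeat the three RSFC tests with participant-specific left and right hippocampus and Pars regions segmented from the existing T1 scans, using the same regions at both sessions. Leave the IPL region unchanged, so that the two versions differ only in Pars and Hipp.
3. Report these beside the MRS-voxel version, which is kept because it matches the tissue of the E/I measure. Limit claims about the hippocampus or Pars to results that agree in both versions. Otherwise describe the result as connectivity of the MRS voxel region.
4. State the region source for the participant with baseline RSFC but no baseline MRS measures, and reconcile technical issues, poor shimming and time constraints as the reasons for that participant's missing data.

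The cost is re-extraction of time series from data already preprocessed, with no new scans. A further FreeSurfer run may be needed, since the plan describes tissue segmentation but not a parcellation into named regions. Step 2 adds three uncorrected exploratory tests, to be labelled as added after the data were seen. If the grey-matter-restricted masks are tested as well as the untrimmed ones, that adds three more (3 + 3 = 6), to be labelled in the same way.
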